Putra et al.⁶ reports that with low bone density, the drilling trajectory might deviate toward the softer part of the bone after the second drilling procedure. Therefore, highest deviation was found in the cases that the bone density was less than 500 Hounsfield unit (HU).

Multiple bone condition predictors like bone density, bone width, and cortical bone thickness significantly influenced the accuracy in implant placement with CGS.

Some other factors like implant site, type of implant (immediate, early or delay), mucosal thickness, graft in the area, quantity of implants have been reported as a factor influencing the accuracy of the guided surgery.^{6,7}

The aim of this cohort prospective study is to assess the influence of clinical and anatomical factors on the accuracy of computer-guided surgery. The following factors will be taken into consideration for the analysis of the data: 1) Implant location (anterior or posterior); 2) Single or multiple implants; 3) Mucosal thickness; 4) Native or regenerated bone, 5) immediate or delay implant.

2. Objectives.

Overall objective.

The aim of this cohort prospective study is to assess the influence of clinical and anatomical factors on the accuracy of computer-guided implant surgery on immediate and delayed implant placement:

Specific objectives:

- 1) To assess the influence of implant location (anterior or posterior) on the accuracy of CGS
- 2) To assess the influence of time for implant placement (immediate or delay) on the accuracy of CGS.
- 3) To assess the influence of type of bone (native or regenerated bone)
- 4) To assess the influence of bone density on the accuracy of CGS.

Hypothesis.

- 1: H1 implant location (anterior or posterior) has an influence on the accuracy of CGS
- 2: H1 The time for implant placement (immediate or delay) has an influence on the accuracy of CGS.
- 3: H0 The mucosal thickness does not have an influence on accuracy of CGS.
- 4: H1 The bone density has an influence on the accuracy of CGS.

Material and methods.

The study will be performed at a private practice (Blasi Dental Clinic) which is under the tutelage of the Universitat Internacional de Catalunya (UIC) CElm.

Moreover, the present study will be registered in clinicaltrials.gov.

For the sample size calculation, we use as reference Putra's¹⁴ article where it is reported correlations between different deflection parameters and bone density. These are weak-moderate magnitude correlations (0.3<r<0.5).

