The sample size was calculated for 3 levels of statistical power, a 95% confidence level with Pearson's linear correlation coefficient null test)

Degree of correlation Power reached

	70%	80%	90%
r=0.3 (weak)	67	84	112
r=0.5 (moderate)	23	29	37

To detect a weak magnitude correlation as significant, 84 patients will be needed for this study.

Inclusion criteria.

- Patients between 25 to 60 years old.
- Periodontally stable patients. Adequate oral hygiene with less than 15% Full Mouth Plaque Score (FMPS).
- Patients who need dental implant treatment without simultaneous regeneration.
- Ability to follow instructions and availability to attend for regular compliance during the entire study.
- With presence of partial edentulism (at least 6 remaining teeth distributed in the dental arch to support the guide).

Exclusion criteria:

- Active infections

- Untreated periodontal disease
- Heavy smokers (>10 cigarettes per day)
- Drug / Alcohol dependency
- Medical condition contraindicating implants dependency
- Patients under bisphosphonate therapy
- Limited mouth opening

All the information will be given to the patients before sign and obtain the informed consent form.

Clinical procedures.

After assessing the fulfillment of the inclusion criteria, pre-operative cone beam computed tomography (CBCT) (Newtom, Cefla S.C.) and intraoral digital impressions (Trios®, 3Shape Dental Systems, Denmark) will be obtained for each patient to achieve a digital wax-up and a presurgical plan for the exact position of the implants by a single calibrated operator (RP).

Every patient could have a maximum of four implants to be placed (one per quadrant), in those cases, there will be one guide per implant.

The digital imaging and communications in medicine (DICOM) files will be imported to a guided-surgery planning software (Codiagnostix, Dental wings) to perform an implant planning based on the digital wax up; in this step the assessment of the mucosal thickness will be performed using the STL and the DICOM files superimposed. The measurement will be taken from the crestal bone until the soft tissue surface (mm).

Furthermore, a surgical guide will be designed, and 3D printed (SprintRay Pro S; SprintRay Inc) with implant guide resin (SprintRay EU Surgical Guide Clear; SprintRay Inc) by RP for the surgical procedure, supported by the whole dental arch, and reinforced with one bar across the arch.

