Through guided surgery, previously planned and designed based on CBCT study and CAD/CAM scanning, placement of Conelog Progressive line implants

(Biohorizons Camlog, Iberia) will be performed in maxilla or mandibula in a one stage surgery by a 8 years' experience operator (GB).

Implant placement will be fully guided and a postoperative CBCT in ECO mode ($35\mu\text{Sv}$) will be taken after the implant placement to assess the final position.

Both CBCT will be aligned (pre-op scan and post-op scan) to make calculations by a single evaluator (AB) included the following (Fig. 1): (1) angle: angle deviation measured in degrees; (2) base: deviation at implant shoulder in millimeters; (3) tip: deviation at implant apex in millimeters; (4) 3D offset: global deviation in 3D directions in millimeters; (5) mesiodistal deviation in millimeters: (+) deviated to the distal direction and (-) deviated to the mesial direction; (6) buccolingual deviation in millimeters: direction: (+) deviated to lingual direction and (-) deviated to buccal direction; and (7) apicocoronal deviation in millimeters: direction: (+) deviated in the apical direction. and (-) deviated in the coronal direction.

[figure not shown]

Figure 1. Parameters to evaluate de position of the implant. ¹⁴

Clinical and study schedule

The estimated appointments for all patients:

- Screening visit: Selection, recruitment of patients, and signing of informed consent.
- First visit: Data collection (intraoral scanning and CBCT acquiring).
- Second visit: Implant placement and post-operative CBCT.

Ethics

This protocol follows the ethical principles regarding human experimentation recommended by the World Medical Association in the Declaration of Helsinki.

After fulfilling the inclusion criteria, all patients will receive a full informed consent.

After evaluation and clarification of possible concerns, the patient will return the signed consent as an agreement of participation.

Statistical analysis.

A descriptive analysis will perform by analyzing the mean, standard deviation, minimum, maximum values, and median for each outcome. For a 95% confidence level and an estimated standard deviation, T-test and Pearson's linear correlation coefficient null test will be used to analyze the data.

Study limitations

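### One mucosal-thickness rule covers immediate and delayed sites but probably measures different tissue at each, so a pooled Hypothesis 3 correlation can carry a timing effect or dilute a real one

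*Combined protocol and SAP*

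**What the plan says.** - **Measurement (Clinical procedures).** Thickness is read at the planning stage from the pre-operative files: "in this step the assessment of the mucosal thickness will be performed using the STL and the DICOM files superimposed". The rule is "The measurement will be taken from the crestal bone until the soft tissue surface (mm". No separate landmark is given for immediate sites.
- **Population (Overall objective).** The study concerns "accuracy of computer-guided implant surgery on immediate and delayed implant placement".
- **Hypotheses.** Number 2 is "The time for implant placement (immediate or delay) has an influence on the accuracy of CGS". Number 3 is "H0 The mucosal thickness does not have an influence on accuracy of CGS".
- **Schedule (Clinical and study schedule).** "First visit: Data collection (intraoral scanning and CBCT acquiring", then "Second visit: Implant placement and post-operative CBCT". No extraction appointment is listed.
- **Data form (Annex b).** There is one thickness field in mm, with no reference point and no code for not applicable. A separate yes/no item records whether the implant is immediate.
- **Analysis (Statistical analysis).** "T-test and Pearson's linear correlation coefficient null test will be used to analyze the data". No stratification or adjustment is mentioned, and neither test is assigned to a hypothesis.

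**The concern.** At a healed site, crest to soft-tissue surface is the thickness of the mucosa covering the ridge. At a site where the tooth is still in place, no mucosa covers the crest along the planned implant position. The only soft-tissue surface the rule can reach is the gingiva beside the tooth. Both numbers go into the same field under the same name.

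The recorded value may therefore differ between immediate and delayed sites because of what is measured, not because of how thick the mucosa is. Hypothesis 2 expects the outcome to differ along the same division. A variable that shifts with timing, correlated with an outcome that shifts with timing, shows an association even when thickness does nothing within either group. Conversely, if thickness matters only at healed sites, adding values of another kind weakens the correlation. Either way, Hypothesis 3 could be answered wrongly, and a single undifferentiated number would not show afterwards what had been measured.

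**Working it through.** **The plan's own figure.** For r = 0.3, 80% power and two-sided 5%, Fisher's z with the small-sample term gives

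n = [(1.960 + 0.842) / (atanh 0.3 + 0.3/(2 × 83))]² + 3 = (2.802 / 0.3113)² + 3 = 83.98,

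which rounds up to the stated 84. The same formula reproduces the other five cells of the table. The sample size is not in question here. It was set on correlations with bone density.

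**Inputs that the documents do not give (assumptions).**
- One site per patient, 84 sites.
- Share immediate, q: 20%, 30% or 50%.
- Recorded thickness: mean 2.5 mm at delayed sites, and 3.5 or 3.0 mm at immediate sites; SD 0.8 mm in both. The standardised shift dm is 1.0/0.8 = 1.25 or 0.5/0.8 = 0.625.
- Timing shifts deviation by dy = 0.5 SD, with 0.2 and 0 as alternatives.
- No association between thickness and deviation within either timing group.

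**Correlation created by pooling.** With v = q(1 − q),

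r = v·dm·dy / √[(1 + v·dm²)(1 + v·dy²)].

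Base case, q = 0.3, dm = 1.25, dy = 0.5: v = 0.21, so

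r = 0.1313 / √(1.3281 × 1.0525) = 0.1313 / 1.1823 = 0.111.

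**Rejection rate.** Under Fisher's z the mean of the test statistic is atanh(0.111) × √81 = 1.00. The two-sided 5% test rejects with probability 1 − Φ(1.96 − 1.00) + Φ(−1.96 − 1.00) = 0.17. Simulation with 4,000 trials gives 16.5%.

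| Share immediate | Timing effect (SD) | Rejection, 1 mm shift | Rejection, 0.5 mm shift |
|---|---|---|---|
| 20% | 0.5 | 12% | 7% |
| 30% | 0.5 | 17% | 9% |
| 50% | 0.5 | 22% | 10% |
| 30% | 0.2 | 7% | – |
| any | 0 | 5% | 5% |

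For the 0.2 SD row: r = 0.21 × 1.25 × 0.2 / √(1.3281 × 1.0084) = 0.045, and rejection is 7%. With dy = 0 the numerator is zero, so no artefact arises.

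**Dilution.** Suppose r = 0.3 at delayed sites, 0 at immediate sites, and no timing effect. The pooled correlation is (1 − q) × 0.3 / √(1 + v·dm²). At q = 0.3 and dm = 1.25 this is 0.21 / 1.152 = 0.18, and power at n = 84 falls from 80% to about 38–40%.

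**Two remedies compared.**
- *Delayed sites only.* False positives return to about 5%. Power for r = 0.3 is Φ(0.3095 × √(n − 3) − 1.96): about 70% at n ≈ 67 (20% immediate), 64% at n ≈ 59 (30%; 65% in simulation), and 49% at n = 42 (50%).
- *All sites, adjusted for timing by partial correlation.* False positives are 4.9–5.0% in simulation. Power is 79% if r = 0.3 holds in both groups, but only 49–50% at 30% immediate if thickness acts at delayed sites alone.

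Neither remedy is better in every case. Adjustment removes the timing artefact but does not make gingival height a measure of ridge mucosa.

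**The case against.** Four points on the other side carry weight.

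1. *Tooth presence is inferred.* The documents do not define immediate, and the schedule is a three-line list of estimated appointments. The contents of the flow chart and timeline annexes were not available in the text reviewed. This stands as a limit on certainty. The inference is still the ordinary one, and the rule gives no landmark for immediate sites in any case.
2. *The rule does return a value at a dentate site.* It ends at a soft-tissue surface, so crest to adjacent gingiva follows it. A reader might infer that such sites would be entered as 0 mm, which would create a much larger artefact. The documents do not support that, because a zero entry would not follow the rule. Zero-entry scenarios are therefore left out here.
3. *Tissue beside the site may matter.* The Introduction's stated mechanism is that mucosal thickness and mobility affect how the guide seats. Gingival height at immediate sites is thus not shown to be irrelevant. This also stands: it is a different quantity, not a worthless one, and removing those sites from every analysis is not justified.
4. *The Pearson test is not assigned to Hypothesis 3.* That is correct. Thickness is continuous, so it is the natural choice of the two tests named, and neither is adjusted.

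Unadjusted confounding by timing is a general weakness of the plan. What is specific to thickness is that the measured quantity itself changes with timing.

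**Conclusion.** The point holds in a conditional form. Followed as written, and on the usual meaning of immediate, the plan records two different quantities in one field and names only unadjusted tests. If they are pooled, the Hypothesis 3 correlation can carry a timing effect when timing affects deviation, or can dilute a real effect at healed sites.

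The size cannot be fixed from the documents. At 30% immediate and a 1 mm shift, the nominal 5% test rejects in about 17% of trials with a 0.5 SD timing effect and about 7% with 0.2 SD. With no timing effect there is no inflation. The base-case artefact, r of about 0.11, is well below the r = 0.3 used for design.

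A reader might go further and conclude that the answer to Hypothesis 3 cannot concern mucosal thickness at all. That does not follow. With few immediate sites, a small shift or a weak timing effect, the distortion is slight. The change is worth making because it is cheap and must be settled before measurement begins.

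**What to change.** **Clinical procedures.** State the landmark for each site type. Suggested text: *At delayed sites, ridge mucosal thickness is the distance in mm between bone crest and mucosal surface at the planned implant axis. At immediate sites, gingival height at a stated landmark beside the tooth is recorded as a separate variable.* Define immediate and delayed, and say whether the tooth is present at the scan. Give the data form a field for each quantity.

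**Statistical analysis.** Suggested text: *The correlation of tissue thickness with deviation is estimated separately in delayed and immediate sites, identified from the timing item on the form. The delayed-site estimate answers Hypothesis 3 for ridge mucosa. A partial correlation adjusted for timing, over all sites, is a supporting analysis.*

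**Cost.** A few sentences and one form field; no new scan or visit. The delayed-site estimate uses fewer sites, and the protocol should state the resulting power for r = 0.3: about 65% at 30% immediate and 49% at 50%. Keeping 84 delayed sites at one per patient would need 84/0.7 = 120 or 84/0.5 = 168 patients in total. If that is not feasible, report the estimate with its confidence interval and acknowledge the lower power.

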This clinical study presents some limitations to be taken into considerations. First, if the surgical guide could not fit properly, present movements or break during the procedures, Second, the need of taking two CBCT in one month can represent a topic to be aware. And finally, the data should permit the correct alignment for further analysis and evaluation and its quality must be enough to facilitate the data analysis.

Contingency plan.

Rewarding the mishap of the fitting of the guide, in those cases we will print two guides per case, to have a backup if the first guide breaks. If the guides are not fitting properly, the patient should be excluded from the study.

[figure not shown]
For this study we will use the ECO mode which only presents a minimum effective dose of 9 μ Sv (four times less radiation than a regular CBCT and almost the same radiation as an orthopantomography)

Moreover, if any of the data collected presents any error that could interfere in the data analysis, the patient will be excluded for the study.

Annexes

- a. Flow chart
- b. Patient data collection
- c. Timeline

a. Flow chart

b. Data collection

PATIENT DATA COLLECTION	
PATIENTS PRE-SURGICAL INFORMATION	
Patient number: _____	
Age: _____	
Sex: _____	
Medical conditions _____	
Allergies: _____	
Smoker: Yes _____ No _____ How many per day? _____	
Site of implant placement: _____	
Immediate implant? Yes _____ No _____	
Native bone? Yes _____ No _____	
Single or multiple implants? _____	
Mucosal Thickness (millimeters) _____	
Bone Density (Hounsfield units) _____	
Complications with the surgical guide? Yes _____ No _____	
Other complications _____	

c. Timeline of study

Glosario de términos.

- 1. Computer-guided surgery (CGS)**
- 2. Cone beam computed tomography (CBCT).**
- 3. 3-Dimensional (3D)**
- 4. Hounsfield unit (HU).**
- 5. Full Mouth Plaque Score (FMPS).**

Investigador Principal [name]

Fdo: [name]

IP or tutor signature

Supporting researcher:

--	--

2.

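### Implants go into both jaws but jaw enters no analysis, so the unadjusted location and bone-density results can carry a maxilla–mandible difference if jaw is linked to both the factor and the deviation.

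*Combined protocol and SAP*

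**What the plan says.** Clinical procedures states that placement "will be performed in maxilla or mandibula in a one stage surgery". It adds: "Every patient could have a maximum of four implants to be placed (one per quadrant", so one patient can contribute implants in both jaws. The eligibility criteria neither restrict nor balance jaw.

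The aim at the end of the Introduction lists the factors for analysis: "1) Implant location (anterior or posterior); 2) Single or multiple implants; 3) Mucosal thickness; 4) Native or regenerated bone, 5) immediate or delay implant". Jaw is not among them. It is also absent from the four specific objectives and the four hypotheses. The two results most exposed are objective 1 ("To assess the influence of implant location (anterior or posterior) on the accuracy of CGS") and objective 4 ("To assess the influence of bone density on the accuracy of CGS").

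The Statistical analysis section names descriptive statistics, a t-test and a Pearson correlation, with no covariate, stratification or multivariable model. Study limitations does not mention jaw. The data form in Annex b has one open line, "Site of implant placement", with no coding rule and no separate jaw field.

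The Introduction does treat site as relevant to accuracy: "Some other factors like implant site, type of implant (immediate, early or delay), mucosal thickness, graft in the area, quantity of implants have been reported". It does not name jaw.

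**The concern.** This is an observational study in which site is not assigned. Anterior and posterior sites may have different shares of maxillary implants, and density may differ between the jaws. If deviation also differs between jaws, the planned comparisons mix the two effects, and nothing in the plan would separate them. The result could be a false finding or a masked one, depending on the direction.

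At stake are hypothesis 1 (location) and hypothesis 4 (density). Density matters most, because a density correlation is the basis of the sample size. The gap is also not closed by simply moving to an adjusted analysis: a model built from the five listed factors would still leave jaw out.

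**Working it through.** **The plan's own figure.** The sample-size table is for r = 0.3 and 95% confidence. Fisher's z, n = ((1.960 + 0.842)/atanh(0.3))² + 3, gives 84.9. With a t-based critical value and bias correction it gives 84.1. The plan states 84, so the figure reproduces (two-sided). It covers an unadjusted correlation only.

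**What must be assumed.** The documents give no jaw shares, jaw differences in deviation or density, or SD. All values below are assumptions.

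**Location t-test.** Assume 34 anterior and 50 posterior sites, within-jaw SD 0.6 mm, independent sites and no true location effect. With maxillary shares pA and pP and a jaw difference D:

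- bias = (pA − pP) × D
- SE² = [0.36 + D²pA(1 − pA)]/34 + [0.36 + D²pP(1 − pP)]/50
- rejection ≈ 1 − Φ(1.96 − bias/SE) + Φ(−1.96 − bias/SE)

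| pA v pP | D (mm) | Bias (mm) | SE (mm) | Rejection |
|---|---|---|---|---|
| 60% v 50% | 0.3 | 0.03 | 0.137 | about 5.5% |
| 70% v 50% | 0.2 | 0.04 | 0.135 | about 6% |
| 80% v 50% | 0.3 | 0.09 | 0.137 | 10% |
| 90% v 50% | 0.4 | 0.16 | 0.138 | about 21% |

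Simulation with 40,000 runs per row agrees to within a percentage point. With jaw added to the model, rejection returns to about 5% in every row.

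**Density correlation.** Assume 60% maxillary, a jaw gap of d SD in density and e SD in deviation, and no density effect within jaw. Then

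r = d·e·0.24 / √[(1 + 0.24d²)(1 + 0.24e²)], where 0.24 = 0.6 × 0.4.

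- d = 0.5, e = 0.3: r = 0.036/√(1.06 × 1.0216) = 0.035. At n = 84, rejection is 6%.
- d = 1, e = 0.5: r = 0.12/√(1.24 × 1.06) = 0.105. Rejection is 16%.

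**Wider range.** Equivalently, spurious r = (density–jaw correlation) × (jaw–deviation correlation). Correlations of 0.2–0.6 and 0.2–0.5 give r from 0.04 to 0.30 and rejection from 6.5% to 80%. The top of that range needs both links to be strong at once.

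**Precision cost of adjusting density.**

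- If the partial correlation is itself 0.3, 80% power needs 85 or 86 patients by the two methods above, against 84.
- If instead the density slope and residual SD stay fixed, the d = 1 case implies a density–jaw correlation of √(0.24/1.24) = 0.44 and a variance inflation of 1/(1 − 0.44²) = 1.24. The effect 0.3/√(1 − 0.09) = 0.314 shrinks to 0.314 × √(1/1.24) = 0.282, a partial r of 0.282/√(1 + 0.282²) = 0.272. Power at n = 84 is Φ(atanh(0.272) × √80 − 1.96), about 70%, against about 80% unadjusted. Restoring 80% would take about 105 patients.

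**The case against.** **The documents never say that jaw affects accuracy.** This is true. They name implant position, site, density, bone width and cortical thickness, and the last two are also missing from the factor list and the form. The point is therefore conditional. It still stands as one about design: the plan treats site as relevant, keeps one axis of it, and has no way to check the other.

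**It overlaps with the lack of any adjusted model.** Partly so. Adding jaw to the factor list without a model would only add another unadjusted comparison. But an adjusted model using the listed factors would still omit jaw, so jaw has to be named.

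**The bias may be negligible.** In the mild cases it is: 5.5–6% against a nominal 5%. Even the larger density case gives an r of about a third of the design value of 0.3.

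**Adjusting density for jaw could change the question.** If jaw acts on accuracy only through density, the density correlation is not confounded, and adjustment merely loses precision. That is a reason to report both results. It is not a reason to avoid adjustment, because jaw does not lie on the path from density to accuracy.

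**Stronger readings that the documents do not support.** A reader might infer that the location and density results will be wrong, but no document figure shows that either link exists. A reader might also infer that the form already holds jaw. The site field is open and uncoded, with one line for up to four implants, and an entry of only anterior or posterior would not give the jaw.

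**Conclusion.** The point holds in conditional form. Both jaws are treated, jaw is in no analysis, and the plan as written cannot tell a jaw difference from a location or density effect. Bias arises only if, in this sample, jaw is linked both to the factor and to deviation.

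Under the stated assumptions the effect runs from trivial to material: a false location difference of 0.03 to 0.16 mm, and a spurious density r of 0.035 to 0.10. These figures treat sites as independent, although the plan allows several per patient. The stated sample size is not in error. This is worth correcting before analysis, and it does not stop the study from running.

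**What to change.** 1. Code jaw (maxilla or mandible) for each implant from the site field. Where that field does not show it, use the planning file or CBCT, which the plan obtains for every patient.
2. Add jaw to the list of factors for analysis in the Introduction.
3. In Statistical analysis, estimate the location effect from a model with location and jaw that allows for several implants per patient.
4. Report the density result both as the planned Pearson correlation and as a jaw-adjusted (partial) correlation.
5. Tabulate the deviations by jaw and location.

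Cost: one derived variable, with no new visits, scans or patients. The price is precision in the adjusted density result. It is equivalent to one or two patients if the partial correlation is 0.3, but a fall in power from about 80% to about 70% at n = 84 if the density–jaw correlation is about 0.44 with slope and residual SD fixed. The planned unadjusted result is kept alongside, so nothing now in the plan is lost.

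### All seven accuracy outcomes rest on one scan alignment by one evaluator, with no masking to the recorded study factors, repeat reading or reliability check described

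*Combined protocol and SAP*

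**What the plan says.** The clinical procedures section gives the outcome step in one sentence: "Both CBCT will be aligned (pre-op scan and post-op scan) to make calculations by a single evaluator". Seven measures follow from it: angle, deviation at the shoulder, deviation at the apex, 3D offset, and signed mesiodistal, buccolingual and apicocoronal deviation. There is no other outcome.

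The word calibrated appears once, earlier in the same section, for the person who prepares "a presurgical plan for the exact position of the implants by a single calibrated operator". That is a different role from the outcome evaluator.

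The study limitations section recognises that the result depends on the superimposition: "the data should permit the correct alignment for further analysis and evaluation". The contingency plan answers this by excluding patients whose data contain an error that could interfere with the analysis. It does not say what counts as such an error, or whether the person deciding knows the patient's factor values.

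The data collection form in the annexes puts site, immediate placement, native bone, mucosal thickness and bone density on one sheet. Nothing says whether the evaluator sees it.

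On sample size, the plan relies on an article in which "it is reported correlations between different deflection parameters and bone density", and concludes: "To detect a weak magnitude correlation as significant, 84 patients will be needed for this study".

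**The concern.** Every deviation is a difference between two superimposed scans, so any error in the superimposition goes straight into the outcome. Two kinds of error matter.

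- **Systematic error.** The hypotheses expect an influence of location, timing and bone density, and none of mucosal thickness. If the evaluator has the form or knows the factor values, small alignment choices could differ between factor levels. The planned t-tests and Pearson tests could not distinguish this from a real effect.
- **Random error.** It tends to weaken correlations and group comparisons. For mucosal thickness, where the hypothesis is stated as no influence, that pulls the result towards the stated hypothesis. For measures without a sign (angle, shoulder, apex and 3D offset appear to be of this kind), random error also pushes the mean deviation upwards. Without a repeat reading, nobody can say how much of a reported deviation is alignment error.

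The exclusion rule deals only with gross failures. Without a criterion, and if applied by someone who knows the factors, it could itself select patients.

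**Working it through.** **Step 1. Reproduce the plan's sample size.** Inputs from the sample-size paragraph and table: "a 95% confidence level with" Pearson's "linear correlation coefficient null test", r = 0.3, power 80%. Sidedness is not stated; two-sided is taken because it reproduces the table, whereas one-sided gives 68.

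n = ((1.960 + 0.842) / atanh(0.3))² + 3 = (2.802 / 0.3095)² + 3 = 84.9

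A version with small-sample bias correction gives 84.07. The stated 84 is reproduced, as are the other five cells of the table within rounding. Power at n = 84 and r = 0.3 is 79.6% (plain Fisher z) or 80.0% (bias-corrected), so there is no reserve.

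**Step 2. What averaging two readings could add.** The documents give no reliability figure. Assume a single-reading reliability R of 0.7, 0.8 or 0.9, and take 0.30 as the correlation observed with one reading. If the errors of two readings correlate at ρ, the mean of the two has reliability

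R₂ = R / (R + (1 − R)(1 + ρ)/2)

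With ρ = 0 this is the Spearman-Brown formula 2R/(1 + R). The correlation becomes 0.30 × √(R₂/R). Power is the bias-corrected value at n = 84.

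| R (assumed) | ρ (assumed) | R₂ | r | Power |
|---|---|---|---|---|
| 0.7 | 0 | 0.82 | 0.325 | 86% |
| 0.8 | 0 | 0.89 | 0.316 | 84% |
| 0.9 | 0 | 0.95 | 0.308 | 82% |
| 0.7 | 0.5 | 0.76 | 0.312 | 83% |
| 0.8 | 0.5 | 0.84 | 0.308 | 82% |
| 0.9 | 0.5 | 0.92 | 0.304 | 81% |

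Example: R = 0.8, ρ = 0.5 gives 0.8 / (0.8 + 0.2 × 0.75) = 0.8 / 0.95 = 0.842, and 0.30 × √(0.842/0.8) = 0.308. This formula suits the signed deviations best. For unsigned measures it is only a guide, because random error also shifts their mean.

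**Step 3. What a systematic shift could do.** Assume no true difference, SD 0.6 mm, a two-sided 5% t-test and groups of 42 and 42. None of these group sizes or SDs is in the documents. The non-centrality is (shift/SD) × √(42 × 42/84) = (shift/0.6) × √21.

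- 0.10 mm: 0.1667 × 4.583 = 0.764, rejection probability 11.7%.
- 0.20 mm: 0.3333 × 4.583 = 1.528, rejection probability 32.7%.
- 0.20 mm with an assumed 20 and 64 split: 0.3333 × √(20 × 64/84) = 1.301, rejection probability about 25%.

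For scale, the introduction cites mean deviations of 1.2 mm at the platform and 1.4 mm at the apex, so 0.10 mm is under a tenth of either.

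**The case against.** Two stronger readings are tempting, and the documents support neither.

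- **That the evaluator is unmasked.** The plan is silent on masking. It does not say that the evaluator holds the factor values. What can be said is that no masking is described.
- **That alignment error dilutes the sized correlation and leaves the study short of power.** The 0.3 comes from correlations reported in a published article, so it already carries that study's measurement error. Power falls below 80% only if the error here is larger than there, and the documents do not allow that comparison. Treating 0.3 as error-free would give 70% power at reliability 0.8, but nothing in the plan supports that premise.

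Other points on the plan's side have weight. Planning, surgery and evaluation are assigned to different people, so the evaluator does not grade their own plan or placement. A single evaluator removes between-reader variation, which is a legitimate choice. Masking can be only partial: location, many immediate sites and grey-level density are visible on the scans being aligned, so for density only the recorded figure can be withheld. The same evaluator re-aligning the same scans may repeat the same errors, which is why the ρ = 0.5 rows are shown. An intra-evaluator ICC would not reveal a systematic bias that the evaluator repeats. Finally, with up to four implants per patient, re-reading everything could mean up to 4 × 84 = 336 further alignments.

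These points limit the claim and the remedy. They leave the gap itself: no masking of what can be masked, and no estimate of measurement error for the study's only outcomes.

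**Conclusion.** The concern holds in a limited form. All the accuracy outcomes depend on one unrepeated alignment by one evaluator. The plan describes neither masking to the recorded factors nor any reliability check, and its exclusion rule has no criterion. This should be changed, because it is cheap and because masking cannot be restored once the readings are made.

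The size is illustrative only. A second reading would add about 1 to 6 percentage points of power at n = 84, depending on the assumed reliability (0.7 to 0.9) and the assumed correlation of the errors (0 or 0.5). An assumed shift of 0.10 mm, with SD 0.6 mm and equal groups of 42, would raise the false-positive rate from 5% to about 12%. The figures do not estimate this study's actual bias, and no deficit against the planned power has been shown.

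**What to change.** 1. Record and lock the factor values before any outcome reading: density in Hounsfield units, mucosal thickness, native or regenerated bone, and timing.
2. Give the same evaluator coded scan pairs in random order, without the data collection form.
3. Have that evaluator repeat the alignment and measurement at least two weeks later. Where all implants are re-read, analyse the mean of the two readings; otherwise repeat at least a random subset.
4. Report the intra-evaluator ICC and the measurement-error SD for each of the seven measures, and state that the ICC does not detect systematic bias.
5. Write down in advance what makes an alignment unusable, and have that decision made without the factor values.
6. State that masking is partial, since location, many immediate sites and grey-level density remain visible.

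The cost is file coding and the same evaluator's time for the second readings, at up to four implants per patient; a random subset keeps this small. No extra assessor, patient, scan or visit is needed.
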